Patients who meet our inclusion criteria will be explained the study aims, protocol, and risks and benefits of participation by a research assistant. They will have a chance to review the consent form and receive a copy if they so choose. Information/Consent forms have been developed in all languages in which the survey is available (Spanish, Portuguese, Haitian Creole, Simplified Chinese, and Traditional Chinese) by certified translators. If needed, Research Assistants will utilize translators to communicate with patients speaking languages other than English. Completing the patient surveys will indicate consent to participate in the study. De-identified informed consent documents will be maintained by the research assistant in a locked folder on-site or on a protected and secure database.

NOTE: When subjects are unable to give consent due to age (minors) or impaired decision-making capacity, complete the forms for Research Involving Children as Subjects of Research and/or Research Involving Individuals with Impaired Decision-making Capacity, available on the New Submissions page on the PHRC website:

<https://partnershealthcare.sharepoint.com/sites/phrmApply/aieipa/irb>

For guidance, refer to the following Partners policy:

Informed Consent of Research Subjects:

[https://partnershealthcare-public.sharepoint.com/ClinicalResearch/Informed Consent of Research Subjects.pdf](https://partnershealthcare-public.sharepoint.com/ClinicalResearch/Informed%20Consent%20of%20Research%20Subjects.pdf)

DATA AND SAFETY MONITORING

Describe the plan for monitoring the data to ensure the safety of subjects. The plan should include a brief description of (1) the safety and/or efficacy data that will be reviewed; (2) the planned frequency of review; and (3) who will be responsible for this review and for determining whether the research should be altered or stopped. Include a brief description of any stopping rules for the study, when appropriate. Depending upon the risk, size and complexity of the study, the investigator, an expert group, an independent Data and Safety Monitoring Board (DSMB) or others might be assigned primary responsibility for this monitoring activity.

NOTE: Regardless of data and safety monitoring plans by the sponsor or others, the principal investigator is ultimately responsible for protecting the rights, safety, and welfare of subjects under his/her care.

All patient and resident data will be de-identified for storage. Data will be stored on a password-protected server. Only the PI and the researchers

will have access to the server. The PI will be responsible for reviewing the data and for the confidentiality of the data.

Describe the plan to be followed by the Principal Investigator/study staff for review of adverse events experienced by subjects under his/her care, and when applicable, for review of sponsor safety reports and DSMB reports. Describe the plan for reporting adverse events to the sponsor and the Partners' IRB and, when applicable, for submitting sponsor safety reports and DSMB reports to the Partners' IRBs. When the investigator is also the sponsor of the IND/IDE, include the plan for reporting of adverse events to the FDA and, when applicable, to investigators at other sites.

NOTE: In addition to the adverse event reporting requirements of the sponsor, the principal investigator must follow the Partners Human Research Committee guidelines for Adverse Event Reporting

Research assistants will be advised to notify the patient's attending physician if the patient divulges suicidal or homicidal ideation during the survey. Otherwise, there are no anticipated opportunities for discovery of incidental findings. If any subject feels uncomfortable and wishes not to participate, they will be able to speak with the PI at any time and/or withdraw from the study with no consequences for their participation in their residency program nor their ability to receive care at our participation institutions.

MONITORING AND QUALITY ASSURANCE

Describe the plan to be followed by the principal investigator/study staff to monitor and assure the validity and integrity of the data and adherence to the IRB-approved protocol. Specify who will be responsible for monitoring, and the planned frequency of monitoring. For example, specify who will review the accuracy and completeness of case report form entries, source documents, and informed consent.

NOTE: Regardless of monitoring plans by the sponsor or others, the principal investigator is ultimately responsible for ensuring that the study is conducted at his/her investigative site in accordance with the IRB-approved protocol, and applicable regulations and requirements of the IRB.

The focus groups will be facilitated by two study staff. The digital recorders used to record the focus groups will be securely stored in the Center for Surgery and Public Health, and transcriptions will be stored in a secure, password-protected database. The virtual focus group data will be recorded and saved digitally on a Mass General Brigham encrypted computer and stored in a secure, password-protected database.

Data collection and monitoring will be coordinated across the 8 AMCs through a multimedia approach. Video teleconferencing will be utilized and a

website will be created to ensure smooth coordination and scheduling of the PACTS curriculum across the sites. Each site investigator will be responsible for managing research assistants and data collection at their institution. Survey data (such as patient surveys, resident pre- and post-tests, and OSCCE scoring) will be collected via a Partners-hosted REDCap survey. Data will be stored in a secure location at each AMC and will be accessed by the research assistant, who will be trained to enter the de-identified data into the secure, password-protected database. The Project Director will have access to the unique IDs assigned to the subjects, but the individual site co-investigators will not. There are no anticipated limitations to confidentiality.

For guidance, refer to the following Partners policies:

Data and Safety Monitoring Plans and Quality Assurance

https://partnershealthcare-public.sharepoint.com/ClinicalResearch/DSMP_in_Human_Subjects_Research.pdf

Reporting Unanticipated Problems (including Adverse Events)

https://partnershealthcare-public.sharepoint.com/ClinicalResearch/Reporting_Unanticipated_Problems_including_Adverse_Events.pdf

PRIVACY AND CONFIDENTIALITY

Describe methods used to protect the privacy of subjects and maintain confidentiality of data collected. This typically includes such practices as substituting codes for names and/or medical record numbers; removing face sheets or other identifiers from completed surveys/questionnaires; proper disposal of printed computer data; limited access to study data; use of password-protected computer databases; training for research staff on the importance of confidentiality of data, and storing research records in a secure location.

NOTE: Additional measures, such as obtaining a Certificate of Confidentiality, should be considered and are strongly encouraged when the research involves the collection of sensitive data, such as sexual, criminal or illegal behaviors.

The focus groups will be recorded through digital voice recorders or virtual via secured web-based video conference software. After the focus groups, the recorders will be stored securely within the Center for Surgery and Public Health for transcription. All patient and resident data will be de-identified for storage. Data will be stored on a password-protected server. Only the PI and the researchers will have access to the server. The PI will be responsible for reviewing the data and for the confidentiality of the data.

Resident subjects' performance on surveys and simulated clinical encounters will be kept confidential through de-identification of the data. All residents in the program will receive the training and will be required to

participate in the interactive learning sessions as a quality improvement initiative; residents' divulging of information during these sessions will be kept private in the confines of the didactic sessions that are restricted to surgical trainees.

Patients will be surveyed face-to-face in private hospital rooms, and patient participants will have the opportunity to include a legally authorized representative in the interview if desired. No minors will be included in the study.

SENDING SPECIMENS/DATA TO RESEARCH COLLABORATORS OUTSIDE PARTNERS

Specimens or data collected by Partners investigators will be sent to research collaborators outside Partners, indicate to whom specimens/data will be sent, what information will be sent, and whether the specimens/data will contain identifiers that could be used by the outside collaborators to link the specimens/data to individual subjects.

Not applicable.

Specifically address whether specimens/data will be stored at collaborating sites outside Partners for future use not described in the protocol. Include whether subjects can withdraw their specimens/data, and how they would do so. When appropriate, submit documentation of IRB approval from the recipient institution.

Not applicable.

RECEIVING SPECIMENS/DATA FROM RESEARCH COLLABORATORS OUTSIDE PARTNERS

When specimens or data collected by research collaborators outside Partners will be sent to Partners investigators, indicate from where the specimens/data will be obtained and whether the specimens/data will contain identifiers that could be used by Partners investigators to link the specimens/data to individual subjects. When appropriate, submit documentation of IRB approval and a copy of the IRB-approved consent form from the institution where the specimens/data were collected.

For the purposes of research dissemination, de-identified and aggregate data will be shared from external AMCs with Partners sites. These data will be shared on password-protected, secure servers at BWH.

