Cover Page for ClinicalTrials.gov

Official Study Title:

Evaluation of a Cultural Dexterity Training Program for Surgeons: The PACTS Trial

NCT Number:

NCT03576495

Document:

Study Protocol

Document Date:

September 18, 2020

**PARTNERS HUMAN RESEARCH COMMITTEE
PROTOCOL SUMMARY**

Answer all questions accurately and completely in order to provide the PHRC with the relevant information to assess the risk-benefit ratio for the study. Do not leave sections blank.

PRINCIPAL/OVERALL INVESTIGATOR

[name], MPH

PROTOCOL TITLE

The Provider Awareness and Cultural Dexterity Toolkit for Surgeons (PACTS) Trial

FUNDING

1R01MD011685-01A1

VERSION DATE

September 18, 2020

SPECIFIC AIMS

Concisely state the objectives of the study and the hypothesis being tested.

Racial disparities in surgical care have been well-documented. In response to the IOM's 2003 recommendations on taking a multi-pronged approach to alleviating disparities that includes cultural competency training, we have proposed cultural dexterity, rather than cultural competency, as a modality for imparting such training to surgical residents. The purpose of this protocol is to test the impact of this new curriculum, called Provider Awareness Cultural Dexterity Toolkit for Surgeons (PACTS), on surgical residents' cross-cultural knowledge, attitudes, and skills surrounding the care of diverse patients, as well as patient-reported and clinical outcomes for patients treated by surgical residents undergoing this training.

1. Aim 1: Evaluate the impact of PACTS on surgical residents' knowledge and attitudes about caring for culturally diverse patients using a pre- and post-assessment.
Hypothesis 1: Residents receiving PACTS will show greater improvement in knowledge and attitudes compared to those who did not.
2. Aim 2: Determine the impact of PACTS on surgical residents' cross-cultural skills as demonstrated in a simulated clinical setting, using an Objective Structured Clinical Examination (OSCE) and by self-report. Each OSCE station will assess one of the four core topics covered by the PACTS training.

Hypothesis 2: Residents receiving PACTS will demonstrate greater improvements in cross-cultural skills.

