3. Aim 3: Assess effectiveness of PACTS on improving clinical outcomes and patient-reported outcomes. We will survey patients cared for by residents enrolled in the study on: (1) satisfaction with pain management, (2) physician communication, (3) trust and (4) comprehension of informed consent. In addition, we will use data from the National Surgical Quality Improvement Program (NSQIP) to measure surgical complications, length of stay, 30-day mortality, morbidity, and readmissions for all patients.

Hypothesis 3: Patients cared for by residents who have completed PACTS will exhibit better clinical and patient-reported outcomes.

BACKGROUND AND SIGNIFICANCE

Provide a brief paragraph summarizing prior experience important for understanding the proposed study and procedures.

Minority patients experience worse overall health outcomes, and these disparities are especially apparent in the costly, high-risk specialty of surgical care. To address this, the National Institute on Minority Health and Health Disparities (NIMHD) collaborated with the American College of Surgeons (ACS) to establish research priorities for surgical disparities. One of the top priorities was to evaluate the effect of improvement in culturally dexterous care on surgical outcomes for patients from disparity populations. Adverse outcomes for minority patients, including patients with limited English proficiency, have been demonstrated because of poor patient-provider communication. We propose that such deficiencies in communication contribute to treatment errors, inadequate pain management, less patient-centered care, decreased adherence to treatment plans, and worse overall clinical outcomes. Additionally, studies have illustrated the preponderance of pro-White implicit biases, which are unconscious, automated preferences that individuals may not even be aware of, among surgeons.

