To evaluate the impact of PACTS on surgical residents' knowledge and attitudes about caring for diverse patients, we will use a pre- and post-test in the form of validated instruments that assess knowledge, attitudes, and self-reported skills on a Likert-type scale. This pre- and post-test will be piloted among a group of surgical residents (N=40) to assess the survey length and clarity of questions. Residents will be recruited using a convenience sampling method from those who participated in the surgery focus groups at ASC 2019. Exclusion criteria from this pilot will be residents at one of the trial AMCs.

Resident skills will also be objectively assessed through an Objective Structured Clinical Examination (OSCE) that will be created by the study

staff and administered immediately before the intervention and within 1-6 months after the intervention has been completed. The OSCE uses 5-point Likert scale questions to evaluate resident performance across multiple domains. A Standardized Patient evaluator and a third-party trained impartial observer will evaluate the residents on these domains, and the resulting numerical scores will be averaged. It will serve both a summative and educational purpose in this context. Due to the COVID-19 pandemic, in order to adhere to social distancing protocols, the OSCE may also be delivered virtually using a secured web-based video-conference software.

We have also developed a novel survey instrument to assess resident knowledge, attitudes, and self-reported skills. This instrument is adapted from pre-existing, validated instruments such as the Cultural Competence Health Practitioner Assessment (CCHPA), developed by the National Center for Cultural Competence, and modified to be relevant to surgical training and practice. Residents will be required to take a knowledge survey before and after receiving the PACTS curriculum or standard training. Attitudes regarding the importance of facing cross-cultural health care situations will be assessed across multiple domains using a novel survey instrument that is based on a survey that was used in a similar curriculum aimed at medical students, as well as the Values and Belief Systems domain.

Patients

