Cover Page for ClinicalTrials.gov

Official Study Title:

Evaluation of a Cultural Dexterity Training Program for Surgeons: The PACTS Trial

NCT Number:

NCT03576495

Document:

Statistical Analysis Plan

Document Date:

June 6, 2017

PACTS ANALYSIS PLAN: The multi-year cluster-randomized study design will enable us to examine differences between and within the Early Intervention and Control/Delayed PACTS training groups across three unique time points (Year 2 pre-intervention, Year 2 post-intervention and Year 3 post-intervention). Details of statistical measures/methods and power calculations appear below.

Within-group differences (repeated measures).

Repeated measure differences on dichotomous outcomes will be examined using Chi-square and Fisher's exact tests, as well as unadjusted logistic regression models controlling for resident-specific demographic factors (e.g. age, IAT, post-graduate year, and sex).

Differences in ordinal outcomes (e.g. three- or five-point Likert scale reporting or ordered category scores) between pre- and post-intervention testing will be examined using Chi-square tests, unadjusted ordered logistic regression, and ordered logistic regression adjusted for resident- and program-specific factors. Table 7 depicts our sample size/power calculations, according to which we will be able to detect an 11% absolute difference in the proportion achieving "adequate" vs. "sub-optimal" dichotomized assessments before and after PACTS training. This accounts for an up to 20% sample loss from the expected 200 enrolled residents per group.

Between-group differences (independent measures). Pre- vs. post- differences in both self-reported and observer-assessed ordinal outcomes between the Early and Delayed Intervention groups will be assessed at the end of the first training period using Chi-square tests and unadjusted ordered logistic regression, as well as ordered logistic regression models controlling for resident- and program-specific factors. Previous work demonstrated that exposure to training similar to PACTS was associated with a 20-25% increase in the proportion of trainees achieving "adequate" scores on an OSCE-based assessment. Based on the number of residents in each arm (n=200), we anticipate that we will be able to detect a much smaller between-group difference even with up to 20% sample attrition over time (Table 7).

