Pre- and post-intervention patient-reported satisfaction and NSQIP outcomes. Management of pain will be assessed using elements of the Pain Treatment Satisfaction Scale (PTSS).¹⁴⁰ Previous work by Gupta et al suggests that, on average, 63% of patients provided assessments of pain control satisfaction in the upper quintile of a standardized 10-point satisfaction scale.¹⁴¹ Subsequent to the intervention, it is estimated that 73% of patients treated by PACTS-trained residents will report satisfaction in the uppermost PTSS quintile. We expect an 8% decrease in readmissions, from 23% to 15% post-intervention. Pre-post intervention differences in patient-reported satisfaction and NSQIP outcomes will be assessed using Chi-square, Fisher's exact tests, or t-tests as appropriate, and ordinal scale differences will be assessed using Chi-Square tests and ordered logistic regression, both without adjustment and controlled for patient-, clinician-, and facility-level factors. It is important to note that the patient groups represent independent samples, and these pre- and post-intervention measures are independent measures, not repeated measures (Table 8). To achieve this, we will recruit 100 patients per site for each data collection phase. Thus, we will collect 300 patients per site over the entire study (2,400 total), giving ample power for both patient and clinical outcomes.

Table 7. Sample Size Calculations

Example Measure	Proportional Difference to be Measured	Expected Minimum Number of Participants Per Group	Minimum Detectable Difference (80% power and $\alpha=0.05$)
Sample size/power calculations for repeated measures			
Within group resident knowledge/skills/attitudes	Pre- vs. Post-test proportion achieving "Adequate" vs. "sub-optimal" dichotomized assessments	Pre-intervention: 160 Post-intervention: 160 (Repeated Measures)	Pre-intervention: 50.0% Post-intervention: 61.0% Thus, we expect to be able to detect a proportional absolute difference of 11% for within-group assessments.
Sample size/power calculations for independent measures.			

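### No primary outcome, deciding model or multiplicity rule is named; Aim 3, with one hypothesis over 9–10 outcomes, is the most exposed

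*Protocol*

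**What the plan says.** The protocol's Specific Aims give three aims, each with its own directional hypothesis.

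- **Aim 1** concerns knowledge and attitudes, and **Aim 2** concerns skills by OSCE and self-report. The resident tests are "validated instruments that assess knowledge, attitudes, and self-reported skills on a Likert-type scale". For the OSCE, "Each OSCE station will assess one of the four core topics covered by the PACTS training". The two raters' scores are averaged, but neither document says whether the stations are pooled for analysis.
- **Aim 3** has the hypothesis "Patients cared for by residents who have completed PACTS will exhibit better clinical and patient-reported outcomes". Its patient-reported outcomes are "1) satisfaction with pain management, (2) physician communication, (3) trust and (4) comprehension of informed consent". Its clinical data come from NSQIP, to "measure surgical complications, length of stay, 30-day mortality, morbidity, and readmissions for all patients". The patient part of Research Design and Methods gives a second, illustrative clinical list, which adds unplanned reoperations and omits readmission.

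For ordinal resident outcomes compared between arms, the SAP lists "Chi-square tests and unadjusted ordered logistic regression, as well as ordered logistic regression models controlling for resident- and program-specific factors". For patient-reported and NSQIP outcomes it lists chi-square, Fisher's exact or t-tests as suitable, and for ordinal scales chi-square and ordered logistic regression, with and without adjustment. Table 7 presents its rows as example measures under one column heading, "Minimum Detectable Difference (80% power and $\alpha=0.05". Neither document designates a primary outcome, a testing order, a deciding analysis or any multiplicity adjustment.

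**The concern.** A hypothesis of better outcomes is not testable until someone says which outcomes must improve, in which comparison and by which analysis. Aim 3 leaves all three open. Its SAP section speaks of pre–post differences, while Table 7 heads the patient block as both within-group and between-group. The two clinical lists differ, so even the set of outcomes is not fixed. For residents, the within-group section describes a logistic model as unadjusted and also lists covariates for it.

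Once the data are in, an analyst cannot fill these gaps without the results influencing the choice. What is at stake is whether a claim that PACTS improved patient or clinical outcomes carries the error rate that a reader will take from the 0.05 in Table 7.

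**Working it through.** **1. What the 0.05 means.** Table 7 does not state sidedness, so I recovered it from the sample sizes. The two-proportion formula is n = [z(α)·√(2p̄q̄) + 0.842·√(p₁q₁ + p₂q₂)]² / (p₁ − p₂)².

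- Readmission, 23% against 15%: p̄ = 0.19, so n = [1.960·√0.3078 + 0.842·√0.3046]² / 0.08² ≈ 376.3, rounded up to 377, as in Table 7. One-sided 0.05 gives 297.
- Residents between arms, 50% against 65.5%: 159, as in Table 7. One-sided gives 125.
- Pain satisfaction, 63% against 73%: 361 with a continuity correction, as in Table 7 (341 without). One-sided with correction gives 288.

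The level is therefore two-sided 0.05, which puts 0.025 in the direction favouring PACTS.

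**2. Outcomes per hypothesis.**

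- Aim 3: 4 patient-reported + 5 clinical = 9, or 10 with unplanned reoperations.
- Aim 1: knowledge and attitudes = 2.
- Aim 2: OSCE and self-reported skills = 2 if the stations are pooled.

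**3. Chance of at least one nominally significant result when nothing differs.** Assume independent outcomes and one test each. The formula is 1 − (1 − a)^k, with a = 0.05 for either direction and a = 0.025 for benefit only.

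| Family | k | Either direction | Favouring PACTS |
|---|---|---|---|
| Aim 3 | 9 | 1 − 0.95⁹ = 37.0% | 1 − 0.975⁹ = 20.4% |
| Aim 3 | 10 | 1 − 0.95¹⁰ = 40.1% | 1 − 0.975¹⁰ = 22.4% |
| Aim 1, or Aim 2 pooled | 2 | 1 − 0.95² = 9.8% | 1 − 0.975² = 4.9% |

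**4. Effect of correlation.** The documents give no correlations, so these are assumptions. Simulation was run for 14 outcomes, the count across all aims with the OSCE pooled. A common correlation of 0.3 lowers the either-direction figure from 51% to 44%, and 0.5 lowers it to 35%. The benefit-only figure falls from 30% to 23% and 17%. The Aim 3 figures would fall in the same way.

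**5. Effect of choice.** Step 3 allows one test per outcome. Picking among models, contrasts or time points after seeing results raises the error, by an amount that the documents do not allow to be calculated.

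**6. Clustering.** The sizes in step 1 reproduce with formulas for independent observations. As an illustration, take the between-arm resident row with 160/4 = 40 residents per site and an assumed intracluster correlation of 0.01 to 0.05. The design effect is 1 + 39 × 0.01 = 1.39 to 1 + 39 × 0.05 = 2.95, and power falls from 80% to about 66% and 37%, before any allowance for having only eight sites.

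**The case against.** The strongest reply is that the documents adopt no rule under which any single significant result proves an aim. They are silent. Hypothesis 3 joins clinical and patient-reported outcomes with an *and*, so it could be read as needing a result in each group. Under independence that would give 18.5% (1 − 0.95⁴) × 22.6% to 26.5% (1 − 0.95⁵ to 1 − 0.95⁶), or 4–5% in either direction. This reply stands as far as it goes: the size of the problem depends on a rule that has not been written. It does not remove the problem, because the conjunctive rule is not written either, and the choice of contrast and model remains open.

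Several stronger readings are tempting and are not supported:

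- **A false-success rate of about 50% for the trial.** Pooling all 14–17 outcomes gives 51–58%, but that merges three separately stated hypotheses, assumes independence and counts harm as well as benefit. The pooled benefit-only figure is 30–35%. Neither is the error rate of any hypothesis in the protocol.
- **Every outcome tested three ways.** The chi-square, unadjusted and adjusted list clearly applies to ordinal outcomes. For NSQIP outcomes the SAP names a test as suitable, and the adjustment clause may attach only to the ordinal scales.
- **0.05 as the stated criterion for each outcome.** It appears only in a sample-size header. Using it per outcome is a fair inference, since no other level is given.
- **Four OSCE endpoints, or an OSCE endpoint that Table 7 sizes.** No analysis text treats the stations separately, and Table 7's resident rows cover knowledge, skills and attitudes generically.

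**Conclusion.** The point holds, chiefly for Aim 3. A plan with no primary outcome, deciding contrast, deciding model or multiplicity handling leaves a hypothesis over 9–10 outcomes without a defined error rate. The Aim 3 figures in the working rest on independence, one two-sided 0.05 test per outcome and no true effect on any of them; they indicate exposure and are not an error rate that the plan states. Aims 1 and 2 need the same clarification but carry much less risk while the OSCE is analysed as one score. This should be corrected, and it does not call the design into question.

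**What to change.** Amend the SAP before results are seen:

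- Treat each aim as its own family, and name its deciding outcome, contrast and single model.
- Aim 3: use the two outcomes that Table 7 already sizes, tested in fixed order at two-sided 0.05, for example the pain-satisfaction proportion and then readmission. Table 7 sizes both as pre–post comparisons, so if a between-arm contrast is chosen the power must be worked out again.
- Aims 1 and 2: name one year-1 between-arm resident outcome each, for example the pooled OSCE score for Aim 2. Keeping the aims separate means that a failed resident test does not block Aim 3.
- Make one model that accounts for site the deciding analysis, with the other listed tests supportive.
- Settle the list of clinical outcomes. Report all remaining outcomes as secondary, with estimates and 95% confidence intervals and no confirmatory claim.

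The cost is SAP wording. Secondary outcomes cannot carry a confirmatory claim, and the second Aim 3 test counts only if the first succeeds. The ordering costs the first test no power. The site-aware model is a separate matter: Table 7 makes no allowance for clustering, so its 80% should be recalculated and not carried over.
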